10.4 Planned recruitment rate

The target minimum sample sizes are as follows:

Clinicians for outpatient study: minimum 25, target 50

Clinicians for observation substudy: 5

Patient consultations for observation substudy (at least 2 pre and 2 post for each clinician, total 20)

Clinicians for inpatient study: minimum 25, target 50

Inpatient clinicians for interview: 5

The clinician participants will be recruited over a short period of time (a few weeks) via clinical meetings. As per the study timeline diagram, patient participants would be recruited from eligible clinics. As this is a qualitative study only a small sample is required (5 clinicians for each substudy for Feasibility study of 'MiADE' point of care natural language processing, EDGE number 157134, IRAS number 322887, Protocol, Version 1.1, DATE 24/07/2023 33/46

interview, and 2 outpatient consultations per clinician pre and post). Patients are seen on a single visit so there should be minimal loss to follow up, and clinicians will be easy to reach as they will most likely still be working at the Trust.

10.5 Randomisation methods

Not applicable - randomisation will not be used.

10.6 Statistical analysis

10.6.1 Summary of baseline data and flow of participants

Descriptive statistics on clinician characteristics (e.g. seniority, specialty) and patient characteristics (e.g. age distribution, gender, ethnicity) will be calculated.

10.6.2 Primary outcome analysis

For the outpatient study, multilevel Poisson regression will be used to calculate the ratio of counts of structured data entries between pre-MiADE and post-MiADE, with the clinician (clinic code) as a random effect to account for clustering by clinician. This analysis will also yield an estimate of the variability of the effect by clinician.

For the inpatient study, the primary outcome will be the difference in proportion of ICD-10 coded diagnoses recorded in the problem list comparing pre-MiADE and post-MiADE. This measure will be calculated separately for each inpatient team and then summarised as an overall difference in proportions, combining data from the different teams. For the inpatient study it will not be possible to differentiate results from patients seen by different clinicians within a team.

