Trial design and methods:	The trial consists of two non-randomised intervention substudies with before and after comparison (outpatient and inpatient), with embedded qualitative substudies involving clinician interviews and (in the outpatient setting only) observed consultations and patient interviews. Clinicians will be recruited, consented and provided with training to use the MiADE system. The system will be switched on at a particular time point, and clinical records for patients seen before and after the system was switched on will be compared. The primary outcome will be the comparison of the number of diagnoses, medication and allergies entered in a structured way per	

	patient. A rapid ethnography-based approach will be used to observe a subset of patient consultations to find out how clinicians are using the system, and semi-structured interviews will be held with patients and clinicians to understand the effect of social, cultural and behavioural information on human experiences and practices.
Trial duration per participant:	5 months
Key Study milestones	Jul 2023: Clinician recruitment and consent
	Aug 2023: Training of clinicians, surveys and observed consultations without MiADE
	Sep 2023: MiADE switch on
	Oct 2023: Interviews, surveys and observed consultations with MiADE
	Nov 2023: Study end
	Dec 2023 – Jan 2024: Data analysis
Estimated total trial duration:	7 months
Planned trial sites:	Single-site, UCLH
Total number of	Outpatient study:
participants planned:	Clinicians using MiADE: at least 25, target 50
	Patients for analysis of pseudonymised health record: estimated 3000 (assuming 25 clinicians each see 5 new patients per week, and 24 weeks of data are analysed)
	Clinicians for observed consultations and interview: 5
	Patients for observed consultation and interview: at least 20 (10 before MiADE, 10 after MiADE)
	Inpatient study:
	Clinicians using MiADE: at least 25, target 50
	Patients for analysis of pseudonymised health record: estimated 600 (assuming 5 inpatient teams each discharge 5 patients per week, and 24 weeks of data are analysed)
Main inclusion/exclusion criteria:	Electronic health record of patients being seen in clinics under the care of participating clinicians
Statistical methodology	Outpatients: comparison (pre- and post-intervention) of mean

Feasibility study of 'MiADE' point of care natural language processing, EDGE number 157134, IRAS number 322887, Protocol, Version 1.1, DATE 24/07/2023

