4. TRIAL DESIGN

This study consists of two substudies (inpatient and outpatient studies), each of which is a nonrandomised intervention study with before and after comparison. The outpatient study also includes an embedded qualitative substudy for a subset of consultations, with patient and clinician interviews. A subset of clinicians will also be interviewed for the inpatient study. The overall clinician participant flow is illustrated in Figure 2.

[figure not shown]

Figure 2: Study flow diagram showing how clinicians will move through the study

Three time periods will be analysed. The primary comparison will be for recording of structured information in patient records between pre-MiADE and post-MiADE periods once clinicians have been consented into the study, as they will have received training and the comparison will show the change in behaviour that results from the system being available. There is a possibility that structured recording may improve because of the study itself (i.e. a Hawthorne effect), so a prior 8week period will also be studied in order to evaluate this effect. See figure below for the overall trial design and timing of interventions. The overall study timeline is shown in Figure 3.

The MiADE system will be made available according to clinician-level permissions, which can be switched on or off. This will allow clinicians' use of problem lists and other structured data to be compared before and after the system is switched on. There will be a period of at least 4 weeks between clinicians entering the study and having the MiADE system switched on.

[figure not shown]

Figure 3: Study timeline

Training programme

All clinicians in the study will undergo a standardised training package consisting of viewing a video and reading a user guide, with access to help from the research team by email or phone throughout the study. The training will cover:

- The importance of maintaining problem lists with accurately coded information about a patient's diagnoses
- National and local (UCLH) guidance on the use of problem lists
- How to use the MiADE system
- The aims and methods of the study

Clinicians will not be eligible to enter the study and have the MiADE system switched on for their EHR user profile until they have undertaken the training.

Pre-MiADE questionnaire – questions for all clinicians

- What is your seniority (e.g. FY1, Consultant etc.)?
- What is your specialty?

Pre-MiADE questionnaire – outpatient study

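### The outpatient pre/post ratio has no allowance for calendar time, so a steady drift in structured recording would be read as an effect of MiADE

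*Protocol*

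**What the plan says.** The milestones in the Protocol's study summary read "Jul 2023: Clinician recruitment and consent", then "Aug 2023: Training of clinicians, surveys and observed consultations without MiADE", then "Sep 2023: MiADE switch on", then "Nov 2023: Study end". Section 10.4 adds: "The clinician participants will be recruited over a short period of time (a few weeks) via clinical meetings". Section 7.2 describes a single-arm before-and-after study.

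Section 10.6.2 fixes the outpatient primary analysis: "multilevel Poisson regression will be used to calculate the ratio of counts of structured data entries between pre-MiADE and post-MiADE". The only other term named is a clinician random effect. Section 4 gives the contrast a causal reading: "the comparison will show the change in behaviour that results from the system being available".

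An 8-week period before consent is also extracted. Section 10.6.4 uses it in two separate two-period comparisons: before consent versus before MiADE, read as the Hawthorne effect, and before consent versus after MiADE, read as the effect of the whole programme. Calendar drift and season are not mentioned.

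**The concern.** If every clinician moves from baseline to MiADE at about the same date, the ratio measures MiADE plus whatever else changed over those weeks. Section 4 attributes all of it to the system, which requires an assumption of no concurrent time trend. The Protocol neither states nor examines that assumption.

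Drift is plausible here. The baseline starts around training that stresses the importance of problem lists, and the effect of that training may fade or build. Section 10.6.4 describes institutional support for quality improvement, which need not stop at switch-on. Upward drift would inflate the ratio and downward drift would hide a real effect. The primary objective is whether MiADE increases structured recording, and section 1 says the findings will support roll-out.

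**Working it through.** **Inputs from the Protocol.** Gap from study entry to switch-on: at least 4 weeks (section 4). Post-MiADE period: 8 weeks (section 4, Study 1). Pre-consent period: 8 weeks (section 4). Weeks analysed: 24 (summary), which fits 8/8/8; the minimum gap gives 8/4/8. Volume: 25 clinicians × 5 new patients = 125 per week. Planning effect: 62% to 70%, with 8.8 problems per patient (section 10.3).

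**Assumptions.** Drift rates, since the Protocol gives none. Entries per patient of 8.8 × 0.62 = 5.46, carried over from the audit figures as section 10.3 does for its own outpatient calculation. This affects the standard errors but not the ratios.

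**The plan's own figure.** Two-sided 5% and 80% power are not stated but reproduce it: [1.96√(2×0.66×0.34) + 0.842√(0.62×0.38 + 0.70×0.30)]² / 0.08² = 549 problems per group, and 549/8.8 = 62 patients. The corresponding ratio is 70/62 = 1.129.

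**False ratio with no MiADE effect.** Ratio = (1+g)^d, where g is weekly drift and d is the distance between period midpoints: (4+8)/2 = 6 weeks or (8+8)/2 = 8 weeks.

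| Drift per week | 4-week baseline (d = 6) | 8-week baseline (d = 8) |
|---|---|---|
| +0.5% | 1.03 | 1.04 |
| +1% | 1.06 | 1.08 |
| −1% | 0.94 | 0.92 |

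To produce the whole 1.129, drift must be 1.129^(1/6) − 1 = 2.0% or 1.129^(1/8) − 1 = 1.5% per week.

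**Chance of declaring a difference at 1% drift and no effect.** Weekly entries are 125 × 5.46 = 682. The standard error of the log ratio is √[(1/4 + 1/8)/682] = 0.023 or √[(1/8 + 1/8)/682] = 0.019. The chance is 0.73 (4-week) or 0.99 (8-week). If the variance is three times the mean, it is 0.32 or 0.67.

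**What the planned secondary comparisons would show at 1% drift.** Before consent versus before MiADE has midpoints (8+4)/2 = 6 or (8+8)/2 = 8 weeks apart and gives 1.06 or 1.08, the same as the false MiADE ratio. Before consent versus after MiADE has midpoints 12 or 16 weeks apart and gives 1.01^12 = 1.13 or 1.01^16 = 1.17, so it is more exposed.

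**Segmented model.** Terms: a step at consent/training, a linear week trend, and a step and slope change at switch-on. The effect is the average post-switch-on level against the projected earlier trend. In units of one week's variance, unadjusted variance = 1/n_pre + 1/8 and adjusted variance = 1/n_pre + 1/8 + d²/S. S is the sum over the two earlier periods of n(n²−1)/12, which is 42 for 8 weeks and 5 for 4 weeks.
- 8/4/8: 0.375 + 36/47 = 1.141; √(1.141/0.375) = 1.74.
- 8/8/8: 0.250 + 64/84 = 1.012; √(1.012/0.250) = 2.01.

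Under 1% drift and no effect, the model returns 1.000. With no drift and MiADE uptake rising linearly over 8 weeks to a mean ratio of 1.13, it keeps about 1.13. A model with one common slope through all three periods returns only 1.036 (8/4/8) or 1.040 (8/8/8), because it treats gradual uptake as background trend.

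**What the model cannot do.** With an assumed 8% seasonal step at switch-on, every model tried still returns 1.080. With an assumed 15% training boost halving every 3 weeks and no MiADE effect (8/4/8), the planned ratio is 0.936 and the segmented one about 0.95.

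**The case against.** The study is openly a non-randomised feasibility study, and the lack of a concurrent control is a declared design limit. It already adds a third period against one alternative explanation. Extra model terms and sensitivity analyses are often left to a statistical analysis plan, which is not shown. The drift rates have no support in the documents. All of this stands, and it is why the point is an inexpensive improvement and not a reason to replace the primary analysis. It does not remove the point, because the Protocol itself fixes the contrast, its causal reading and a different role for the earlier period.

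A reader might infer more than the documents support:

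- *That season can also be checked.* It cannot. The extract covers about 24 weeks of one year, from participating clinicians only.
- *That no planned analysis would reveal drift.* The before-consent versus before-MiADE comparison would show it; the difficulty is the label and the lack of any link to the primary result. The audit-log acceptance data in section 10.6.3 also help: more entries without accepted suggestions would point away from MiADE.
- *That every baseline falls in summer and every MiADE period in autumn.* The milestones are only month-level, and the pre-consent window reaches back to about May. Section 4 says "The MiADE system will be made available according to clinician-level permissions, which can be switched on or off", and section 7.7 ties the trial's end to the last clinician switched on, so some stagger is possible. Inpatient rotation dates are not given, so the timing argument is confined to the outpatient study.
- *That attribution should depend on the adjusted estimate.* That estimate is much less precise and does not fully handle a non-linear fading training effect, so it should not act as a gate.

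**Conclusion.** The point holds for the outpatient primary analysis. As written, the ratio cannot distinguish MiADE from a steady concurrent drift, and section 4 claims more than the comparison can show. At an assumed 1% per week the false ratio is 1.06 to 1.08, roughly half or more of the planned 13% increase. The direction and size of any real drift are unknown. The conclusion rests on the month-level milestones being followed, baselines of 4 to 8 weeks, and approximately steady drift. The extract can support a check for drift, but not for season.

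**What to change.** 1. Keep the planned ratio in 10.6.2 as primary.
2. Add to 10.6.4 a segmented Poisson sensitivity analysis over all three periods, with the clinician random effect, a step at consent/training, a linear calendar-week trend, and both a step and a slope change at switch-on. Report the average post-switch-on ratio against the projected earlier trend beside the planned ratio, with no rule making attribution depend on it.
3. State in 10.6.4 that the before-consent versus before-MiADE comparison reflects calendar drift as well as any Hawthorne effect.
4. Reword the section 4 sentence to say that the comparison shows the change associated with switch-on, assuming no concurrent time trend.
5. State as a limitation that season cannot be separated from MiADE with this extract.

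The cost is wording and one extra model, using dates already in the extract. The adjusted standard error is about 1.7 times (8/4/8 weeks) to 2.0 times (8/8/8 weeks) the unadjusted one, and a fading, non-linear training effect is only partly removed. Switching clinicians on in batches would give a concurrent comparison, but it would need an amendment and more time. It is optional and not needed for this fix.

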10.3 Sample size calculation

Based on a prior audit [15], 62% of problem list entries were entered as structured data and there were mean 8.8 problems per patient. In order to detect an increase from 62% to 70%, 549 problems are required in each group, which is 62 patients (assuming 8.8 problems per patient). This study aims to recruit at least 5 inpatient teams who would each discharge at least one inpatient per day, giving 100 patients in a 4-week period.

For outpatients, assuming each clinician sees 5 new patients each week, they will see 20 patients in a 4 week period. Using the same calculation as for inpatients, a sample size of only 5 clinicians is required to investigate the primary endpoint. However, a larger sample (target = 25) will be used in order to assess variability between clinicians.

For the patients in the qualitative substudies, there is no technique for formal sample size estimation. The number of observed clinicians (5 for inpatients and 5 for outpatient) and number of outpatient observations pre and post MiADE (2 per clinician per phase) has been selected to have a high probability of demonstrating potential themes. Using the method of Potts et al. [17], with a sample size of 5, assuming random sampling, there is 83% probability of surfacing a theme exhibited by 70% of the population.

The maximum number of clinicians to be recruited has been set at 100 according to the specification of the NLP server intended to be used for this trial.

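### Section 10.6.2 names only a clinician random effect for clustering but promises the variability of the MiADE effect; without a random period coefficient the two do not agree, and the interval for the ratio is too narrow if the effect varies

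*Protocol*

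**What the plan says.** For the outpatient study, Section 10.6.2 says that "multilevel Poisson regression will be used to calculate the ratio of counts of structured data entries between pre-MiADE and post-MiADE". The random part of this model is then described in a single phrase: "with the clinician (clinic code) as a random effect to account for clustering by clinician". So the clinician is the only random term named, and its stated purpose is clustering. The next sentence reads: "This analysis will also yield an estimate of the variability of the effect by clinician".

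Section 10.3 holds that 5 clinicians would be enough for the primary endpoint, but that "a larger sample (target = 25) will be used in order to assess variability between clinicians". Section 10.4 gives the recruitment figures: "Clinicians for outpatient study: minimum 25, target 50".

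Section 10.6.4 plans subgroups by specialty and seniority, and correlations of clinician characteristics with the change in mean entries. It names no other model for how the ratio varies between clinicians.

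**The concern.** A clinician random effect included for clustering is ordinarily a random intercept. Its variance describes how much clinicians differ in their usual level of recording. It says nothing about how much they differ in their response to MiADE, because the model gives all of them the same ratio. A programmer who follows the first sentence literally cannot produce what the second promises.

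The primary interval is affected too. Every clinician contributes to both periods, so differences in recording level largely cancel from the ratio. What does not cancel is the difference in response between clinicians, and a random intercept does not carry it. Some variation is to be expected: the risk table in Section 11 lets clinicians ignore the suggestions or switch the system off. If the effect varies and the model assumes that it does not, the interval for the average ratio is too narrow.

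**Working it through.** **The plan's own figures.** Section 10.3 asks for 549 problems per group to detect 62% versus 70%. Two-sided 5% and 80% power (not stated there, but they fit) give 550, and 549/8.8 = 62.4 patients. The figure reproduces; the point below does not depend on it.

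**Inputs from the protocol**
- Clinicians: K = 25, and 50 as the alternative (Section 10.4).
- Patients: "assuming each clinician sees 5 new patients each week, they will see 20 patients in a 4 week period" (Section 10.3).
- Pre-MiADE period: "There will be a period of at least 4 weeks between clinicians entering the study and having the MiADE system switched on" (Section 4), so at least 5 × 4 = 20 patients per clinician.
- Post-MiADE period: 8 weeks (Section 4, Study 1), so 5 × 8 = 40 patients per clinician.

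**Assumptions, not in the protocol**
- tau, the between-clinician SD of the log ratio: 0, 0.1, 0.2, 0.3.
- Mean structured entries per patient, mu: 1, 2, or 0.62 × 8.8 = 5.46. The last comes from the problem-list audit that Section 10.3 first applies to inpatients. It is not an outpatient count of problems, medications and allergies.
- Exact Poisson variation within clinician and period, so patient-level overdispersion plays no part here.

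**What each model contains.** For clinician j:
- Random intercept: log mean = a + u_j + b × post. The parameters are a, b and the SD of u_j. Nothing describes variation in b.
- Random coefficient added: log mean = a + u_j + (b + v_j) × post. The SD of v_j is tau, the quantity that Section 10.6.2 promises.

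**Standard error of the log ratio.** With total counts Y_pre = 20·K·mu and Y_post = 40·K·mu:
- random-intercept model: SE ≈ sqrt(1/Y_pre + 1/Y_post);
- allowing for variation: SE ≈ sqrt(1/Y_pre + 1/Y_post + tau²/K).

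Since 1/20 + 1/40 = 3/40, the ratio of the second to the first is sqrt(1 + (40/3)·mu·tau²). K cancels, so with patients per clinician fixed the shortfall is the same for 5, 25 or 50 clinicians. Example: mu = 2, tau = 0.2 gives sqrt(1 + 1.067) = 1.44.

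Results for K = 25, with tau = 0.1 / 0.2 / 0.3:

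| mu | Model SE | SE allowing for tau | Factor | 95% coverage, formula | 95% coverage, simulated |
|---|---|---|---|---|---|
| 1 | 0.055 | 0.058 / 0.068 / 0.081 | 1.06 / 1.24 / 1.48 | 93 / 89 / 81% | 94 / 86 / 73% |
| 2 | 0.039 | 0.044 / 0.056 / 0.071 | 1.13 / 1.44 / 1.84 | 92 / 83 / 71% | 91 / 79 / 61% |
| 5.46 | 0.023 | 0.031 / 0.046 / 0.064 | 1.31 / 1.98 / 2.75 | 86 / 68 / 52% | 85 / 62 / 42% |

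The simulated column is for an average log ratio of zero. It generally falls below the formula for two reasons. Clinicians with high counts carry more weight, so fewer than K clinicians effectively contribute. The pooled ratio also drifts upward by about tau²/2 on the log scale (0.3²/2 = 0.045), which is a shift of target rather than an SE error. The formula column isolates the SE.

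A separate maximum-likelihood fit of the random-intercept model (intercept SD 0.5, 400 runs per setting) gave 90/75/64% at mu = 2 and 82/58/37% at mu = 5.46, within five points of the table. At tau = 0 it gave about 95.5% and 96%, as it should.

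If the pre-MiADE period also supplies 40 patients, the shortfall grows: the factors at mu = 2 become 1.18 / 1.61 / 2.14.

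**After the change.** Letting the ratio vary by clinician, through a two-stage approximation to the random coefficient, gave 93.5% to 95.5% coverage in every setting simulated (mu = 2 and 5.46). The SD of the effect also became estimable: the mean estimates were 0.18 and 0.29 for true values of 0.2 and 0.3 at mu = 2.

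**The case against.** The strongest reply is that the protocol never says the random effect is an intercept only. The promise of an effect-variability estimate suggests that a varying effect was intended, and the exact random-effects structure is often left to the analysis plan. This stands in part. A reader might infer that the sponsor has settled on the wrong model, and the text does not support that. But Section 10.6.2 does more than leave a detail open: it names one random term, gives its purpose, and claims an output that the term does not supply.

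A reader might also infer that the rationale for 25 clinicians fails. It does not: Section 10.3 speaks only of variability between clinicians, and a random intercept does estimate that for the level of recording. Nor is variation in response left unexamined. Section 10.6.4 looks at clinician characteristics against the change in entries, and Section 10.6.3 at the distribution of acceptance among clinicians. Neither corrects the primary interval.

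Finally, the lowest coverage figures could be read as expected false-positive rates of 38% or 58% (100 minus 62 or 42). The documents do not support that. Those figures need the audit mean of 5.46 and a large tau; at a mean of 1 they are 14% and 27%. An average ratio of 1 with tau 0.3 also has half the clinicians recording less after switch-on, which non-use alone would not produce. Section 10.6.2 states no test or significance level.

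**Conclusion.** The point holds in this form: the two sentences in Section 10.6.2 do not agree. On the ordinary random-intercept reading, the model cannot give the variability of the effect, and its interval for the ratio is too narrow whenever the effect differs between clinicians. The direction is certain once tau is above zero. The size is not, because both tau and the mean outpatient count are assumptions. Across the range shown, the SE is too small by a factor of 1.06 to 2.75, and simulated coverage runs from about 94% to 42%. At tau = 0 the interval is correct. More clinicians do not remove the shortfall. If a random coefficient was intended all along, the defect reduces to the protocol not naming the term that its promise and its interval depend on.

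**What to change.** In Section 10.6.2, specify a multilevel Poisson model with a random intercept and a random coefficient for period (post- versus pre-MiADE) by clinician. State that the SD of the period coefficient, with its confidence interval, is the estimate of the variability of the effect, and that the confidence interval for the average ratio comes from this model.

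Name a fallback for non-convergence: the common-ratio Poisson model with standard errors robust to clustering by clinician and a small-sample correction. This tolerates a clinician with no entries in one period, for whom a clinician-specific log ratio is undefined. The fallback protects the interval but gives no SD of the effect, and the text should say so.

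The cost is a few lines in Section 10.6.2, carried into the analysis plan, with no new data. The downside is a wider interval for the primary ratio: at a mean of 2 entries and 25 clinicians, the SE rises from 0.039 to 0.056 at tau 0.2 and to 0.071 at tau 0.3.
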